Only the tablet formulation containing the voruciclib malonate salt will be used in the voruciclib plus venetoclax combination group.

Table 3: Dose Cohorts with Combination Voruciclib + Venetoclax (Amendment 11)

Cohort Dose Level	Doses and Schedule
12	voruciclib 50 mg QOD, administered IS _{2w,2w} + venetoclax administered QD × 28 days
13	voruciclib 50 mg QD, administered IS _{2w,2w} + venetoclax administered QD × 28 days
14	voruciclib 100 mg QD, administered IS _{2w,2w} + venetoclax administered QD × 28 days
15	voruciclib 150 mg QD, administered IS _{2w,2w} + venetoclax administered QD × 28 days
16	voruciclib 200 mg QD, administered IS _{2w,2w} + venetoclax administered QD × 28 days
17	voruciclib 250 mg QD, administered IS _{2w,2w} + venetoclax administered QD × 28 days
18	voruciclib 300 mg QD, administered IS _{2w,2w} + venetoclax administered QD × 28 days
19	voruciclib 350 mg QD, administered IS _{2w,2w} + venetoclax administered QD × 28 days

Abbreviation: QOD = once every other day

At the completion of the DLT period for each cohort, decisions to escalate in subsequent cohorts will be guided by SRC review of all available safety data, PK and PD data.

For Cohort 12, the dosing of voruciclib will be Days 3, 5, 7, 9, 11, and 13 of Cycle 1, and Days 1, 3, 5, 7, 9, 11, and 13 of Cycle 2 and beyond.

Dose escalation to the next cohort will be initiated after 3 subjects have completed 1 cycle with no reported DLTs, or after 6 subjects have completed 1 cycle with no more than 1 DLT (as defined in [Section 4.4](#)) and with the approval of the SRC after review of safety from the cohort under review.

Intra-patient dose escalation to the next dose in Cycle 2 or later cycle is allowed at the discretion of the investigator and after consultation with the Sponsor if the next dose level has been declared safe by the SRC. More specifically, a subject enrolled at a dose level X may have their dose escalated to the next dose level X + 1 after completing Cycle 1 without a DLT.

Dose escalation proceeds until assessment of clinical and PK parameters by the SRC establishes the safe BED for voruciclib in combination with venetoclax. More specifically, a voruciclib dose in combination with venetoclax that meets the following criteria:

- DLT not to exceed 1 in 6 patients, overall response rate (ORR) $\geq 30\%$, as compared to historical ORR of 19% with 400-800 mg venetoclax alone in relapsed/refractory AML ([Konopleva 2016](#)), and

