10.4. Safety Analyses

10.4.1. Adverse Events

The incidence of all TEAEs will be tabulated by cohort. These TEAEs will be classified by system organ class and preferred term or by preferred term in descending order of frequency using the Medical Dictionary for Regulatory Activities (MedDRA). For incidence reporting, if a subject reported more than one AE that was coded to the same system organ class or preferred term, the subject will be counted only once for that specific system organ class or preferred term. An overview of AEs, which includes subject incidence of TEAEs, TEAEs by severity, related TEAEs, related TEAEs by severity, SAEs, deaths, and AEs leading to discontinuation, will be presented.

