## 7.6 Handling of Data from Subjects Undergone Dose Modifications

Data from all enrolled subjects will be reported by the original cohort assignment at enrollment unless otherwise specified. For subjects who underwent dose modifications, results will be reported based on the initial dose level.

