## 7.7 Presentation of Efficacy and Safety Results

Analytical results of efficacy will be reported overall and by tumor type (AML and B-cell malignancies) as well as by treatment regimen (monotherapy and combination therapy) as applicable, whereas safety results will be reported overall and by dose cohort, unless otherwise specified.

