### **8.7 Safety Analyses**

Safety will be assessed and relevant parameters will include AEs, serious adverse events (SAEs), laboratory safety tests including hematology (complete blood count [CBC]), serum chemistry; physical examination; vital signs; Eastern Cooperative Oncology Group (ECOG) performance status; and 12-lead electrocardiogram (ECG).

Safety analyses in general will be presented in tabular format with the appropriate summary statistics. Tabulations will be provided by dose cohort for the escalation part and the expansion part, by tumor type, and in total.

All safety analyses will be performed based on Safety Evaluable Set.

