### 8.7.2 Adverse Events (AE)

An AE is any untoward medical event that occurs to a subject following the start of study drug administration, whether or not the event is considered drug-related. Pre-existing conditions are not considered an AE unless the condition worsens by at least one grade following the start of study drug administration. Adverse events will be captured from the first dose of study drug and continue until 30 days after the last dose, or until a subsequent anti-cancer therapy is initiated if this occurs earlier than 30 days after the last study drug dose.

Treatment-emergent adverse events (TEAEs) are defined identically as AEs in this study.

An SAE is an AE that results in any of the following outcomes:

- Death
- A life-threatening condition
- An inpatient hospitalization or prolongation of an existing hospitalization
- A persistent or significant disability/incapacity
- A congenital anomaly/birth defect
- Important medical events that may not be immediately life-threatening or result in death or hospitalization but may jeopardize the patient or may require intervention to prevent one of the other outcomes listed above

Elective hospitalizations not in response to an AE is not considered an SAE. Adverse events constituting an SAE will be reported beginning from the first dose of study drug.

All deaths within 30 days of the last dose of study drug that are an outcome of an AE should be reported. Deaths due to disease progression should be reported as such and not as SAEs..

An overview of AEs will be provided by dose cohort, disease group and in total, summarizing subject incidence of the following information:

- Any TEAEs
- Drug-related TEAEs
- CTCAE grade  $\geq 3$  TEAEs
- Drug-related CTCAE grade  $\geq 3$  TEAEs
- Deaths due to AEs
- Treatment-emergent SAEs
- Drug-related treatment-emergent SAEs

- Dose interruption due to TEAEs
- Dose interruption due to drug-related TEAEs
- Dose reduction due to TEAEs
- Dose reduction due to drug-related TEAEs
- Discontinuation of study drug due to TEAEs
- Discontinuation of study drug due to drug-related TEAEs

The number and percentage of subjects with TEAEs and Grade 3/4/5 TEAEs will be summarized for each dose cohort, tumor type, and in total by SOC and PT. For these summaries, subjects with multiple adverse events will be counted only once per SOC and PT.

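### Adverse events after a within-subject dose change are tabulated only under the starting dose, and no table by dose received is planned

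*SAP*

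**What the plan says.** **Attribution rule.** SAP 7.6: "Data from all enrolled subjects will be reported by the original cohort assignment at enrollment unless otherwise specified". For subjects with a dose modification it adds that "results will be reported based on the initial dose level".

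**Layout of the safety tables.** SAP 7.7: "safety results will be reported overall and by dose cohort, unless otherwise specified". SAP 8.7: "Tabulations will be provided by dose cohort for the escalation part and the expansion part, by tumor type, and in total". SAP 8.7.2: "An overview of AEs will be provided by dose cohort, disease group and in total", and "The number and percentage of subjects with TEAEs and Grade 3/4/5 TEAEs will be summarized for each dose cohort". Protocol 10.4.1 agrees: "The incidence of all TEAEs will be tabulated by cohort". Protocol 10.2 makes the incidence of AEs, including DLTs, the primary endpoint.

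**Dose changes that are allowed.** Protocol 4.3.2, for the combination cohorts: "a subject enrolled at a dose level X may have their dose escalated to the next dose level X + 1", once Cycle 1 is completed without a DLT and the SRC has declared the next level safe. Protocol 4.3.1.2 has the same provision for monotherapy. Protocol 4.8 provides for reductions; for the intermittent monotherapy cohorts it also allows a move to the one-week-on schedule after a Grade 3–4 event in a later cycle.

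**AE window.** SAP 8.7.2 collects AEs until 30 days after the last dose, or until new anti-cancer therapy if that comes first. Time after a dose change is therefore included.

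**The concern.** SAP 7.6 and 7.7 leave room for exceptions, but no section of the SAP uses it for adverse events. There is no table by dose at onset, no cut at the first dose change, and no named field for dose at onset in the AE listing. SAP 8.5 counts subjects with dose increases and reductions but does not link them to events.

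A reader of the TEAE tables will take each row as the toxicity of that dose. For a subject whose dose changed, part of the row describes a different dose. The affected time is Cycle 2 onward. SAP 3.1.2, and Protocol 4.7 for monotherapy, say that the safe and minimum biologically effective dose rests partly on tolerability over at least two cycles. DLT tables cover Cycle 1 only, so the TEAE tables are the main by-dose summary of later toxicity. Protocol 10.1 assumes an average of 4 subjects per dose level, so a single subject can change a row noticeably.

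**Working it through.** The documents give no figure for this effect, the number of subjects escalated, or AE rates by dose. There is nothing to reproduce, and every rate below is an assumption.

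**1. Weight of one subject.** A subject whose only event followed a dose change moves the starting-dose row by 100/n points: 100/3 = 33.3, 100/4 = 25.0, 100/6 = 16.7.

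**2. Lower-dose row when subjects escalate.** Let p be the per-cycle chance of a Grade ≥3 TEAE at the starting dose and q the chance at the next level. Assume 4 cycles, independence between cycles, p = 10%, q = 10–30%, and half the cohort escalating.

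- No escalation: 1 − 0.90^4 = 34.4%.
- Escalated after Cycle 1: 1 − 0.90 × (1 − q)^3.
- Escalated after Cycle 2: 1 − 0.90^2 × (1 − q)^2.
- Row as SAP 7.6 reports it: the mean of the escalated and non-escalated figures.

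| q | Escalated after C1 | Row, half escalated | Escalated after C2 | Row, half escalated |
|---|---|---|---|---|
| 10% | 34.4% | 34.4% | 34.4% | 34.4% |
| 20% | 53.9% | 44.2% | 48.2% | 41.3% |
| 30% | 69.1% | 51.8% | 60.3% | 47.3% |

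Both timings matter. The next level must be declared safe before anyone moves to it. Subjects whose own Cycle 1 opened that level must wait for its first cohort to complete a cycle, so about Cycle 3 is their earliest move. Later enrollees can move at Cycle 2.

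**3. Chance of at least one misplaced subject.** Let f be the share escalated and h the chance of an event over the whole post-escalation period. In a cohort of 4 the chance is 1 − (1 − f × h)^4. With f = 50%: h = 20% gives 1 − 0.90^4 = 34.4%; h = 40% gives 1 − 0.80^4 = 59.0%.

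**4. Higher-dose row.** Escalated subjects are absent from both its numerator and its denominator. Its percentage still describes the subjects enrolled at that dose, including their own later cycles. What is lost is information. Suppose 4 subjects are enrolled at the higher dose, each staying 4 cycles (16 subject-cycles), and 2 of 4 escalate into it. If they move after Cycle 1, 2 × 3 = 6 subject-cycles at that dose are missing, or 6/22 = 27%. If they move after Cycle 2, 2 × 2 = 4 are missing, or 4/20 = 20%.

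**5. Reductions.** The same rule books events after a reduction to the higher starting dose. If the reduced dose is less toxic, that row reads lower than it would had those subjects stayed at the starting dose.

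**The case against.** Grouping by assigned cohort is a legitimate presentation. It avoids the selection that arises when only subjects who tolerated Cycle 1 appear at the higher dose. The study is declared exploratory (SAP 7.9), the affected events still appear in the totals and listings, and dosing data are listed by subject (SAP 8.5). Protocol 10.2 and 9.14.2 also plan exposure-safety analyses, the latter in a separate report. All of this stands, and it is why the cohort tables should be kept. It does not supply an AE table attributed by dose: listings leave that work to the reader, and the exposure-safety report is a different product.

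Four stronger readings are tempting and are not supported.

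- *Low-dose toxicity is inflated.* This holds only if subjects escalate and the next dose is more toxic. With equal rates or no escalation the effect is zero, and reductions act in the opposite direction.
- *The dose-toxicity gradient is flattened at both ends.* Step 4 shows that omitting escalated subjects does not by itself push the higher-dose percentage down.
- *SRC and 3+3 decisions are compromised.* DLTs are Cycle 1 events, and SAP 3.1.1 excludes escalated subjects from the DLT count at the higher dose. The combination criteria in Protocol 4.3.2 are DLTs, response and trough concentration. The SRC reviews accumulating data, and nothing says that it relies on these tables.
- *The Cycle 4 lung event is an example.* Protocol 4.2.1.1 places that subject in the 50 mg daily cohort and does not say that the dose had been increased. Likewise, the cumulative-toxicity wording in Protocol 4.5 concerns the expansion cohorts, which have their own boundary.

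**Conclusion.** The gap is real and limited. As written, the plan attributes AEs after an escalation to the lower starting dose and AEs after a reduction to the higher one, on the primary endpoint, and no planned table corrects this. The expected effect of escalation is a lower-dose row that is too high, provided the next dose is more toxic. The higher-dose row loses information without necessarily being biased.

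On the assumed rates, the lower-dose row lies between no change and about 17 points too high (51.8 − 34.4 = 17.4) with escalation after Cycle 1, or about 13 points (47.3 − 34.4 = 12.9) after Cycle 2. These figures ignore reductions. The actual net direction and size cannot be determined from the documents. DLT tables and dose-escalation decisions are not affected. This is a low-cost improvement to reporting rather than a flaw in study conduct.

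**What to change.** Keep the by-cohort tables. Add to SAP 7.6 and 8.7.2 one supplementary set covering any TEAE, Grade ≥3 TEAEs, SAEs and drug-related TEAEs:

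- **Columns:** schedule, and the most recent voruciclib dose level received at or before AE onset. Events on off-drug days then carry the last level received, both within a cycle and after the last dose.
- **Scope:** escalations and reductions alike.
- **Denominator:** subject-cycles at that level, with the number of subjects contributing. State how a cycle is split if the level changes within it.
- **Before first voruciclib:** in the combination cohorts AEs count from the first venetoclax dose, and voruciclib starts on Day 3 of Cycle 1. Assign events on Days 1–2 to the cohort's assigned level.

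Add dose level at onset as a field in the SAP 8.7.2 AE listing. Leave the DLT tables unchanged.

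The cost is SAP wording, one derived variable and one set of tables; SAP 8.5 already tabulates dose changes and lists administration data. A footnote should say that subjects can appear in more than one column, that escalated subjects are selected for having tolerated Cycle 1, and that toxicity accumulated at an earlier dose may be carried into a later one.

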## 7.7 Presentation of Efficacy and Safety Results

Analytical results of efficacy will be reported overall and by tumor type (AML and B-cell malignancies) as well as by treatment regimen (monotherapy and combination therapy) as applicable, whereas safety results will be reported overall and by dose cohort, unless otherwise specified.

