In Amendment 11, subsequent to determination of the safe and mBED of voruciclib monotherapy in AML subjects, the combination of voruciclib with venetoclax will be evaluated in subjects with relapsed and/or refractory AML (see rationale provided below).

The combination cohorts, beginning at Cohort 12 dose level of voruciclib in combination with venetoclax on an IS_{2w,2w} dosing schedule, will be enrolled as follows:

- Cohort 12: 50 mg once every other day (QOD), administered IS_{2w,2w} + venetoclax administered QD × 28 days
- Cohort 13: 50 mg QD, administered IS_{2w,2w} + venetoclax administered QD × 28 days
- Cohort 14: 100 mg QD, administered IS_{2w,2w} + venetoclax administered QD × 28 days
- Cohort 15: 150 mg QD, administered IS_{2w,2w} + venetoclax administered QD × 28 days
- Cohort 16: 200 mg QD, administered IS_{2w,2w} + venetoclax administered QD × 28 days
- Cohort 17: 250 mg QD, administered IS_{2w,2w} + venetoclax administered QD × 28 days
- Cohort 18: 300 mg QD, administered IS_{2w,2w} + venetoclax administered QD × 28 days
- Cohort 19: 350 mg QD, administered IS_{2w,2w} + venetoclax administered QD × 28 days

Dose escalation to the next cohort will be reviewed by the SRC after 3 subjects have completed 1 cycle with no reported DLTs, or after 6 subjects have completed 1 cycle with no more than 1 DLT. (DLT criteria defined below.) Escalation to a subsequent cohort will depend on demonstrated safety and tolerability within a cohort and with the approval of the SRC.

If the next dose level in the AML combination cohort has been declared safe by the SRC, subjects enrolled at a lower dose level may have their dose escalated to the next dose level after completing Cycle 1 without a DLT (intra-subject dose escalation). For example, a subject with AML enrolled in Cohort 13 (50 mg IS_{2w,2w}) may have the dose increased to 100 mg in Cycle 2 if the dose of 100 mg IS_{2w,2w} was deemed safe in Cohort 14 by the SRC.

Dose escalation proceeds until a real-time assessment of clinical and PK parameters by the SRC establishes the safe and mBED for voruciclib in combination with venetoclax. More specifically, a voruciclib dose in combination with venetoclax that meets the following criteria:

- DLT not to exceed 1 in 6 subjects, overall response rate (ORR) ≥30%, as compared to historical ORR of 19% with 400-800 mg venetoclax alone in relapsed/refractory AML ([Konopleva 2016](#)), and

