- Trough plasma concentration of 1 to 1.5 μM , concentrations shown to be synergistic in combination with venetoclax in preclinical models.

In Amendment 12, the combination of voruciclib with venetoclax will be evaluated in subjects with relapsed and/or refractory AML using a voruciclib intermittent schedule of daily dosing on Days 1–21 in a 28-day cycle, with no voruciclib dosing on Days 22–28 of the cycle, designated as $\text{IS}_{3\text{w},1\text{w}}$. (see rationale below). In Cycle 1, voruciclib dosing begins on Day 3 after completion of venetoclax dose ramp-up. The starting voruciclib dose level on $\text{IS}_{3\text{w},1\text{w}}$ will be 150 mg (i.e., 2 dose levels lower than the dose of 250 mg that was shown to have no DLTs in the $\text{IS}_{2\text{w},2\text{w}}$ schedule). The venetoclax dose will be 200 mg on Days 1–21 and 400 mg on Days 22–28 in a 28-day cycle. In Cycle 1, venetoclax dose ramp-up will consist of venetoclax 100 mg on Day 1, then 200 mg on Days 2–21, then 400 mg on Days 22–28, with voruciclib beginning on Day 3. Dose escalation will follow the same 3+3 design as in the $\text{IS}_{2\text{w},2\text{w}}$ cohorts, and uses the same definition for DLT, MTD, and mBED.

In the $\text{IS}_{2\text{w},2\text{w}}$ dose escalation cohorts, no DLTs have been reported at doses ranging from 50 mg QOD to 250 mg QD, and enrollment was ongoing at the 300 mg dose level at the time of issuance of protocol Amendment 12.

The combination cohorts on $\text{IS}_{3\text{w},1\text{w}}$ will be numbered as listed below:

- Cohort 21: 150 mg QD, administered $\text{IS}_{3\text{w},1\text{w}}$ + venetoclax administered QD \times 28 days
- Cohort 22: 200 mg QD, administered $\text{IS}_{3\text{w},1\text{w}}$ + venetoclax administered QD \times 28 days
- Cohort 23: 250 mg QD, administered $\text{IS}_{3\text{w},1\text{w}}$ + venetoclax administered QD \times 28 days
- Cohort 24: 300 mg QD, administered $\text{IS}_{3\text{w},1\text{w}}$ + venetoclax administered QD \times 28 days
- Cohort 25: 350 mg QD, administered $\text{IS}_{3\text{w},1\text{w}}$ + venetoclax administered QD \times 28 days

Expansion Cohorts

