A Phase 2 study of venetoclax monotherapy in 32 patients with AML (30 with relapsed and/or refractory; 2 newly diagnosed), demonstrated a 19% response rate (2 CR and 4 complete remissions with incomplete hematologic recovery [CRi]) with a median duration of response (DOR) of 48 days. Venetoclax was generally tolerated up to doses of 1200 mg daily (Konopleva 2016). In another study, venetoclax in combination with azacitidine or decitabine in 57 previously untreated elderly AML patients was administered at doses up to 1200 mg. No dose-limiting toxicities (DLTs) were observed, but subjects at the 1200 mg dose had frequent dose reductions due to gastrointestinal (GI) events. Overall, a 61% remission rate was obtained with 14/57 CR and 21/57 CRi (DiNardo 2018).

These data demonstrate that targeted therapy specific for the apoptotic pathway can have significant clinical benefit for patients with both B-cell malignancies and AML. However, despite high response rates, patients are not cured by currently approved therapy and will generally experience disease progression, indicating the need for development of new agents with a complementary mechanism of action that either alone or in combination with venetoclax or other agents enhance disease clearance and circumvent disease resistance.

Myeloid cell leukemia protein 1 (Mcl-1) is a member of the Bcl-2 anti-apoptotic, pro-survival family of molecules that are commonly over-expressed in B-cell malignancies and AML. Overexpression of Mcl-1 is associated with poor prognosis and resistance to therapy. Mcl-1 is not inhibited by venetoclax, which is specific for Bcl-2, and increased expression of Mcl-1 can be a mechanism of resistance for venetoclax therapy. Acquired resistance of lymphoma cell lines to Bcl-2 inhibition in vitro has been shown to involve transcriptional upregulation of Mcl-1 (Yecies 2010). Additionally, non-clinical studies have also demonstrated the ability of Mcl-1 to render AML cells resistant to Bcl-2 targeted agents, and have demonstrated synergy in AML models between agents targeting Bcl-2 with those targeting Mcl-1 expression including cyclin-dependent kinase 9 (CDK9) inhibitors (Pan 2015, Bogenberger 2017, Luedtke 2017).

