4.5. Expansion Cohort and Early Stopping Boundaries for Toxicity

Once the safe and mBED of voruciclib in combination with venetoclax on IS_{2w,2w} and IS_{3w,1w} has been declared in subjects with AML, an expansion cohort of up to 12 additional subjects for each of the 2 voruciclib dose schedules will be enrolled to further characterize the safety, efficacy, PK, and pharmacodynamics of the mBED on IS_{2w,2w} and IS_{3w,1w}.

Sequential boundaries will be used to monitor the rate of unacceptable toxicities in AML subjects enrolled on expansion cohorts, using criteria consistent with those used to define DLTs in escalation cohort subjects, with focus on potential cumulative toxicities over time. If an excessive number of unacceptable toxicities are observed, the SRC will have the option of either halting study accrual or reducing the dose to reduce the level of toxicity. The boundaries at which enrollment into an expansion cohort will be halted or safe and mBED reduced are listed in Table 7. This is a Pocock-type boundary that yields 0.2 or greater probability of crossing the boundary when the rate of DLT/unacceptable toxicity is equal to the acceptable rate of 20% (Ivanova 2005).

Since these boundaries are very conservative, to avoid a high false positive rate in the early stage of the enrollment period due to a small sample size, the Pocock boundary described below will be implemented after 4 subjects have been enrolled; for subjects 1-3 the decision to halt study accrual or reduce the dose will be based on clinical judgment, SRC, and Sponsor.

Table 7: Early Stopping Boundaries for Toxicity – Expansion Cohort

# Subjects	1	2	3	4	5	6	7	8	9	10	11	12
Boundary	-	*	*	3	3	3	4	4	4	5	5	5

*Subjects 1 – 3 will be based on clinical judgement.

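### The planned AML response rate pools all combination doses, both schedules, and escalation with expansion subjects, so no selection-free ORR is specified at the dose that observed responses help to choose.

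*SAP*

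**What the plan says.** **How the dose is chosen.** The Protocol synopsis, Protocol 4.3.2 and SAP 3.1.1 list criteria for the combination mBED. The synopsis has "DLT not to exceed 1 in 6 subjects, overall response rate (ORR) ≥30" per cent, set against the venetoclax-alone rate ("as compared to historical ORR of 19% with 400-800 mg venetoclax alone in relapsed/refractory AML" in Protocol 4.3.2). A PK criterion is added: "Trough plasma concentration of 1 to 1.5" µM. The committee judges these as data accrue. Once the mBED is identified, escalation stops and the expansion may open (Protocol 4.3.2).

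**What the expansion is for.** Under Protocol 4.5, up to 12 further AML subjects on each of IS2w,2w and IS3w,1w "will be enrolled to further characterize the safety, efficacy, PK, and pharmacodynamics of the mBED". SAP 3.1.3 also lists efficacy among the purposes.

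**How efficacy is reported.** SAP 6.3 defines one Efficacy Evaluable Set and does not separate the two parts. SAP 7.7 states: "Analytical results of efficacy will be reported overall and by tumor type (AML and B-cell malignancies) as well as by treatment regimen". SAP 8.6.2.1 gives ORR and the CR/CRi rate by tumor type, by regimen and in total, with a Clopper-Pearson 95% interval. Regimen means monotherapy or combination, so dose level and schedule are not separated. Protocol 10.6 adds no finer breakdown.

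**How safety is reported.** SAP 8.7 makes the split that efficacy lacks: "Tabulations will be provided by dose cohort for the escalation part and the expansion part".

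**The concern.** Responses seen during escalation help decide which dose goes forward. Those same subjects then enter the reported response rate together with the expansion subjects, whose outcomes played no part in the choice. The expansion is the only group that gives a selection-free reading of efficacy at the mBED, and no efficacy analysis is specified for it.

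Two distortions act on the pooled figure. Selection on response pushes it up. Subjects from doses that were not selected dilute it, and pull it down if lower doses are less active. Reading the pooled ORR as the response rate at the mBED could therefore overstate or understate it, and the planned output would not show which. That matters for deciding whether the combination is worth taking further, and for any informal comparison with 19%.

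**Working it through.** **Benchmark.** Protocol section 1 gives 2 CR and 4 CRi among 32 patients: (2 + 4)/32 = 18.75%, which rounds to the stated 19%. The documents give no power or precision figure for ORR.

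**Inputs.** Escalation cohorts have 3 subjects, an optional fourth, or 6 (Protocol 4.1). The ORR threshold is 30%, so the minimum number of responders r is 1 of 3, 2 of 4 or 2 of 6. The expansion is taken as 12. There are eight IS2w,2w levels (Protocol Table 3). True response rates are assumptions, and ORR is treated as the only selector.

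**Step 1: escalation plus expansion at the selected dose.** This table is not planned, but it is the obvious first remedy. With X ~ Bin(n, p) responders in escalation,

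expected ORR = (E[X | X ≥ r] + 12p)/(n + 12).

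At p = 0.19, 12p = 2.28. For n = 3, P(X ≥ 1) = 1 − 0.81³ = 0.469 and E[X | X ≥ 1] = 0.57/0.4686 = 1.216, so the expected ORR is (1.216 + 2.28)/15 = 23.3%.

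| n (r) | P(passes ORR criterion) | E[X given pass] | Expected combined ORR | Excess over 19% | Two-sided 95% CI coverage |
|---|---|---|---|---|---|
| 3 (1) | 0.469 | 1.216 | 23.3% | +4.3 points | 97.4% |
| 4 (2) | 0.166 | 2.150 | 27.7% | +8.7 points | 92.1% |
| 6 (2) | 0.320 | 2.320 | 25.6% | +6.6 points | 96.6% |

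At a true 30% the expected values are 33.1%, 36.6% and 34.3%. The 12 expansion subjects alone average the true rate.

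**Step 2: the pooled figure the SAP plans.** This was simulated with 200,000 runs per scenario. Escalation proceeds through the eight IS2w,2w levels and stops at the first cohort with observed ORR of at least 30%; 12 subjects are added there and all subjects are pooled. The second schedule and the DLT rule were not modelled. Entries are the mean pooled ORR minus the mean true ORR at the selected dose, in percentage points.

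| Assumed true ORR by dose | n = 3 | n = 4 | n = 6 |
|---|---|---|---|
| Flat 19% | +1.0 | +3.6 | +2.1 |
| Flat 30% | +0.6 | +2.0 | +1.2 |
| Rising 2% to 30% | −2.3 | −4.6 | −5.3 |
| Rising 5% to 40% | −1.9 | −5.2 | −4.7 |

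If only the upper four levels can be selected, as a rough stand-in for the trough criterion, the two rising curves give shortfalls of about 5 to 9 points.

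**Step 3: expansion alone.** Under the same selection rule its mean equals the true rate at the selected dose (0.190 at a true 0.19; 0.300 at a true 0.30). Its precision is low: 4 of 12 responders gives a Clopper-Pearson interval of 10% to 65%.

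**The case against.** **The upward bias belongs to a table nobody planned.** A reader might infer that the reported ORR at the selected dose is biased upward by 4 to 9 points. The documents do not support that, because the SAP plans no ORR at any single dose. The Step 1 figures describe a hypothetical by-dose table; the planned figure has no fixed direction of error.

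The trial's documented progress reinforces this. Protocol 4.3.2 reports no DLTs on IS2w,2w up to 250 mg and enrolment under way at 300 mg, so six levels had been passed. Take a flat 19%, six unselected cohorts, selection on ORR at the seventh, and 12 expansion subjects. If the six missed on ORR, the pooled ORR averages 10.6%, 18.3% or 15.0% (n = 3, 4, 6). For n = 3 this is (0 + 1.216 + 2.28)/33. If they missed only on other criteria, it averages 21.0%, 22.5% or 21.2%. This objection stands.

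**The intervals are not generally invalid.** Two-sided coverage in Step 1 falls below 95% only for n = 4, where the fourth subject is optional. This stands too.

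**ORR is not the only selector.** The DLT and trough criteria and committee judgement also apply, so selection on response is probably weaker than modelled.

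**No comparison with 19% is planned.** A reader might infer that the reported ORR will be tested against the benchmark. It appears only in the mBED criterion. SAP 8.6.2.1 plans an estimate and interval, and SAP 7.9 calls the study exploratory. That answers a complaint about error control. It does not explain omitting a description of efficacy in the group enrolled partly to provide it.

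**Existing text does not fill the gap.** SAP 7.6 reports by original cohort unless otherwise specified, but SAP 7.7 and 8.6.2.1 do specify otherwise for efficacy. Subject listings would allow a reader to reconstruct an expansion-only rate, but that is not a planned estimate.

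**Conclusion.** The reporting gap is established from the text. Observed response helps select the combination mBED, and the expansion is enrolled partly to characterise efficacy there. Yet the only planned AML combination ORR mixes all doses, both schedules and both parts. No planned estimate at the mBED is free of the subjects who helped choose it.

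The size is moderate and the direction unknown. As a reading of ORR at the selected dose, the pooled figure is about 1 to 4 points high on average if response is flat at 19%. It is about 2 to 5 points low under the rising curves assumed here, and up to 9 in the restricted variant. The 23.3% to 27.7% for a combined by-dose table is an upper-end illustration. All of these rest on assumed response rates and on ORR as the sole selector. The point warrants a cheap improvement to the SAP and does not call the design into question.

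**What to change.** In SAP 7.7 and 8.6.2.1, add the escalation/expansion split already used in SAP 8.7.

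- Report AML ORR and the CR/CRi rate with Clopper-Pearson 95% intervals for the expansion cohort alone, separately for IS2w,2w and IS3w,1w. Name this the selection-free estimate at the mBED, and the one to use if any descriptive comparison with the 19% historical rate is made.
- Keep escalation plus expansion at the selected dose, and the regimen-level pooled ORR, as supportive summaries. Label both as including the subjects used to select the dose.
- State in the table which responses count. SAP 5.1.2 includes MLFS but not PR for AML, whereas SAP 8.6.2.1 computes ORR from CR/CRi or PR.

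The cost is SAP wording and one additional table, with no new subjects or data. The drawback is precision: the estimate rests on at most 12 subjects per schedule, instead of about 15 to 18 with escalation subjects at that dose included (3 + 12 to 6 + 12). Intervals will be wide, as the 4 of 12 example shows.
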